However, in this ARISTOTLE sub-group analysis, subjects who underwent cardioversion had already been chronically anticoagulated either prior to entry or, if treatment-naïve, as part of the trial. Thus, there was no information on the effectiveness of apixaban in subjects newly presenting with AF who were anticoagulant-naïve and in whom an early cardioversion was indicated, eg, with an image-guided approach or a definite onset of symptoms ≤48 hours. An image-guided approach facilitates cardioversion earlier than the conventional minimum of 3 weeks of anticoagulation that would normally be required prior to cardioversion. It is expected that most image-guided cardioversions would occur from a few hours to a few days after initial presentation. In subjects with a clearly defined onset of symptoms ≤48 hours, guidelines suggest that cardioversion may be performed early without image-guidance.

Therefore, this study is being conducted to assess the effectiveness of apixaban compared with usual care (parenteral heparin and/or oral anticoagulation with Vitamin K antagonist (excluding other novel oral anticoagulants (NOACs)) in subjects with non-valvular AF indicated for early cardioversion and initiation of anticoagulation in a real-world, clinical practice setting. The image guidance approach in subjects with >48 hours or unknown duration and non-guided with symptoms ≤48 hours will be referred to as “early

cardioversion” throughout this protocol. Subjects with symptom onset >48 hours or unknown duration and not following an image guided approach are expected to receive the conventional anticoagulation strategy (minimum of 3 weeks prior to cardioversion) as per guidelines.

The overriding design principle of this study is that of a randomized observational approach, sometimes known as a ‘pragmatic study’, where subjects are managed according to their investigator’s usual care following randomization, and in conjunction with the protocol directed schedule of activities.

Data from 15 completed or on-going Phase 2/3 studies in over 29,000 subjects provide exposure information of apixaban doses ranging from 2.5 mg twice a day (BID) to 20 mg once daily (QD) and treatment durations up to approximately 33 months.

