## **2. STUDY OBJECTIVES AND ENDPOINTS**

The study objective is to assess the occurrence of clinical endpoints in non-valvular AF subjects (ie, without rheumatic mitral valve disease, a prosthetic heart valve, or valve repair) indicated for cardioversion and treated with apixaban or usual care (parenteral heparin and/or oral anticoagulation with Vitamin K antagonist (excluding other NOACs)).

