### **4.1. Inclusion Criteria**

Subject eligibility should be reviewed and documented by an appropriately qualified member of the investigator's study team before subjects are included in the study.

Subjects must meet all of the following inclusion criteria to be eligible for enrollment into the study:

1. Subjects with non-valvular atrial fibrillation (as documented by electrocardiogram (ECG) at Visit 1) indicated for cardioversion and initiation of anticoagulation in accordance with the approved local label. Subjects presenting with atrial flutter with no evidence of atrial fibrillation are not eligible for enrolment.
2. Age  $\geq 18$  years (Age  $\geq 19$  years for Korea only and Age  $\geq 20$  years for Japan only).
3. Evidence of a personally signed and dated informed consent document indicating that the subject (or their legally-recognized representative) has been informed of all pertinent aspects of the study.
4. The subject is willing to provide contact details for at least one alternate person for study staff to contact regarding their whereabouts, should the subject be lost-to-follow-up over the course of the study. (Subject to IRB/IEC approval)
5. Female subjects of childbearing potential must agree to use a highly effective method of contraception throughout the study and for at least 28 days after the last dose of assigned treatment. A subject is of childbearing potential if, in the opinion of the investigator, she is biologically capable of having children and is sexually active.
6. Subjects who are willing and able to comply with scheduled visits, treatment plan, and other study procedures.

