#### **6.5. Guidelines for Image Guidance (eg, TEE/TOE or CT) Suggesting Atrial Thrombus**

The investigator should follow their usual practice, and in accordance with local and national guidelines. Positive TEE/TOE or CT will be submitted for adjudication.

It is expected that in the event of imaging suggesting atrial thrombus, that any cardioversion attempt would be deferred for a minimum period of at least 3 weeks of further anticoagulation, consistent with local/national guidelines. It would also be expected that repeat imaging would take place prior to consideration of further cardioversion attempts.

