2.2. Study Objectives and Endpoints

The study objective is to assess the occurrence of clinical endpoints in non-valvular AF subjects (i.e., without rheumatic mitral valve disease, a prosthetic mechanical heart valve, or mitral valve repair) indicated for early cardioversion and treated with apixaban or usual care (parenteral heparin and/or oral anticoagulation with Vitamin K antagonist (excluding other NOACs)).

Clinical Endpoints

- Stroke.
- Systemic embolism.
- Major Bleeding.
- Clinically Relevant Non-Major Bleeding.
- All cause death.

Additional information will also be collected on:

- Cardioversion details: timing, type, attempts, and rhythm status
- Length of in-hospital stay.
- Use of image guidance e.g., TEE/TOE or CT.

This protocol will use independent adjudication of disease-related clinical endpoints.

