8.2.4. Analyses of Clinical Endpoints

- *Stroke.*
- *Systemic embolism.*
- *Major Bleeding.*
- *Clinically Relevant Non-Major Bleeding.*
- *All cause death.*

The following time periods will be defined for reporting clinical endpoints:

- Pre-cardioversion
- Post-cardioversion
- ALL: entire duration (include 30 days follow-up after cardioversion).

The characterization of stroke, systemic embolism and death will be done based on the adjudicated endpoints during the study (according to an intention-to-treat paradigm). Analysis of these endpoints will be based on the full analysis set.

The characterization of bleeding will be done with a focus on adjudicated major bleeding and clinically relevant non-major bleeding during the treatment period (according to a safety paradigm). Analysis of these endpoints will be based on the safety analysis set.

The clinical endpoint summaries will include descriptive statistics of individual event rates and their exact 95% confidence intervals; however exact risk ratios and corresponding p-values comparing the treatment arms will also be presented without any formal testing.

Sensitivity analysis: If the TEE/TOE or CT procedures will identify subjects with thrombus (thrombus-positive), sensitivity analyses of all clinical endpoints will be run on a dataset obtained by removing those subjects from the Full Analysis Set. The dataset from which thrombus-positive (as per investigator’s assessment) subjects were excluded will be labeled as Full Prevention-Evaluable; its complementary set of Thrombus Positive-ITT will be analyzed for the endpoints of Stroke, Systemic Embolism, and Death. Sensitivity analyses of bleeding events will also be run on a dataset (labeled as Safety Prevention-Evaluable Analysis Set) obtained by removing subjects with thrombus (as per investigator’s assessment) from Safety analysis set; its complementary set of Thrombus Positive-Safety will be analyzed for the bleeding endpoints.

The Modified Full Analysis set will be analyzed for the endpoints of Stroke, Systemic Embolism, and Death.

Subgroup analyses: Clinical endpoints and safety (AEs, SAEs) will be reported for each subgroup of interest. Subgroups of interest are (please note that bleeding endpoints are based on the safety analysis set while the others are based on the full analysis set):

- “Early Cardioversion” (defined as cardioversion that occurs within 7 days from randomization),
- Image Guidance (TEE/TOE or CT),

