- age (< 65 years old, ≥ 65 years old)
- gender.
- For the clinical endpoints (stroke/embolism/death), also analyze by (first) cardioversion status: ‘Interventional cardioversion’, no cardioversion, or ‘Spontaneous cardioversion’
- For clinical endpoints, breakdown summaries by Apixaban initial dose levels (loading dose vs. no loading dose) will be produced.

We will display graphically the Kaplan-Meier product-limit estimators of the time to

- Composite of first adjudicated stroke or systemic embolism,
- First Major bleeding event,
- Composite of first major bleeding and clinically relevant non-major bleeding
- All cause death.

8.2.5. Other analyses:

The full analysis set will be used to summarize data on cardioversion details, length of in-hospital stay and usage of image guidance.

- Cardioversion details will be summarized by number of attempts (a separate table will be presented for each number of attempts).
 - The summary for first attempt will be based on the full analysis set. Timing of cardioversion will be the time from randomization to the first attempt only, with time to first attempt censored at the last day of follow-up if an attempt has not been made.
 - The hazards ratio (and p-value) will be calculated for time from randomization to the first attempt at cardioversion, comparing image guided to non-image guided subjects.
 - The second attempt will be summarized based on the subset of the full analysis set that already had the first cardioversion, etc.

- For each attempt we will summarize the number and proportion of subjects with cardioversion attempts and the number and proportion with each rhythm status.
 - Demog/baseline tables will be subset for 1) subjects with no cardioversion attempt, 2) subjects with one cardioversion attempt, and 3) subjects with 2 or more cardioversion attempts
- Length of in-hospital stay is defined as the number of hours from hospital admission to hospital discharge following cardioversion. The date and time of all hospital admissions and discharges following cardioversion will be captured within the CRF at Visit 2 and 3. Frequency of hospital stay, mean and median duration will be summarized by treatment arm.
 - Early cardioversion is defined as cardioversion that occurred within the first 7 days after randomization. Frequency and proportions will be reported by treatment arm.

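### The SAP's early-cardioversion subgroup is formed by what happens after randomization, differs from the protocol's strategy definition, and has no baseline-defined counterpart

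*SAP*

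**What the plan says.** **Definition in the protocol (1.2).** "The image guidance approach in subjects with >48 hours or unknown duration and non-guided with symptoms ≤48 hours will be referred to as" early cardioversion, and the protocol says the term carries that meaning throughout. No day limit is attached. The same section foresees other subjects in the trial: "Subjects with symptom onset >48 hours or unknown duration and not following an image guided approach are expected to receive the conventional anticoagulation strategy", which means at least 3 weeks before the procedure.

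**Definition in the SAP.** In the subgroup list of 8.2.4, early cardioversion is "defined as cardioversion that occurs within 7 days from randomization". SAP 8.2.5 says again: "Early cardioversion is defined as cardioversion that occurred within the first 7 days after randomization". Neither place refers to the protocol's definition or explains the change.

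**Objective and eligibility.** SAP 2.2, like the protocol summary, has subjects "indicated for early cardioversion and treated with apixaban or usual care". Protocol section 2 has subjects "indicated for cardioversion and treated with apixaban or usual care". Inclusion criterion 1 asks only that they be "indicated for cardioversion and initiation of anticoagulation in accordance with the approved local label".

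**Analyses.** Stroke, systemic embolism and death are analysed in all randomized subjects, and bleeding in all treated subjects (SAP 5, 5.1, 5.3). SAP 8.2.4 plans risk ratios and p-values between arms for the clinical endpoints, reports those endpoints in each subgroup, and does not exempt subgroups from the comparisons.

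**The concern.** Protocol 1.2 justifies the trial by the missing evidence for early cardioversion in anticoagulant-naïve subjects. A reader who meets a table headed early cardioversion will take it to describe that strategy. Under the SAP it describes subjects who reached the procedure by day 7.

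That is a condition on the course after randomization. Subjects managed by the early strategy leave the group when something goes wrong before the procedure, so the group's event rates can be lower than the strategy's. The trial is open label, and the steps before cardioversion differ by arm (protocol 5.2.3.1 and 5.2.3.2). Membership could therefore differ by arm as well, and a risk ratio within the group would then mix treatment effect with selection.

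**Working it through.** **1. The plan's own event figures.** Protocol 9.1 predicts 1 + 3 = 4 strokes or systemic emboli within 30 days after cardioversion: 4/1500 = 0.27%, stated as about 0.3%. For major bleeding, 2 + 5 = 7: 7/1500 = 0.47%, stated as about 0.45%. Both reproduce. The plan gives no figure for the size of the early group.

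**2. Who is early under each rule.**

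| Subject | Protocol 1.2 | SAP 8.2.4 / 8.2.5 |
|---|---|---|
| Image-guided, >48 h, cardioverted on day 3 | early | early |
| Image-guided, >48 h, thrombus seen | early strategy | not early |
| Early strategy, dies before cardioversion | early strategy | not early, by construction |
| Early strategy, stroke or bleed delays the procedure past day 7 | early strategy | not early |
| Conventional strategy, at least 3 weeks first | not early | not early |

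The second row follows from protocol 6.5: with imaging that suggests thrombus, "any cardioversion attempt would be deferred for a minimum period of at least 3 weeks of further anticoagulation". Three weeks is 21 days, beyond the 7-day limit. The SAP does not say whether spontaneous reversion by day 7 counts, so that row is left out.

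**3. Is the strategy isolated elsewhere?**
- The full analysis set contains every early-strategy subject, mixed with conventional-strategy subjects.
- The image-guidance subgroup (SAP 8.2.4) covers one limb in part. It is not limited to >48 h or unknown duration, and imaging use is recorded at Visit 2 (protocol 6.2).
- The non-guided limb with symptoms ≤48 h has no subgroup. Arrhythmia duration appears only as a Cox covariate with an interaction test (SAP 6.4).

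None of these rebuilds the two-limb definition from information fixed at randomization.

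**4. How many image-guided subjects might pass day 7.** Protocol 1.2 gives time to cardioversion in the TEE-guided arm of an earlier trial as mean 3.0, SD 5.6 days. Assume that this timing carries over and is lognormal:
- σ² = ln(1 + (5.6/3.0)²) = 1.50, so σ = 1.225
- μ = ln(3.0) − 1.50/2 = 0.348
- P(time > 7) = 1 − Φ((ln 7 − 0.348)/1.225) = 1 − Φ(1.30) = 0.096

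That is about 10%, for the image-guided limb only.

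**5. How few events the group would hold.** The share cardioverted within 7 days is not in the documents. Assume 30% to 90% of 750 per arm, which is 225 to 675. Scaling the step 1 predictions by that share gives 0.3 to 0.9 strokes or emboli on apixaban and 0.9 to 2.7 on usual care.

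**6. What selection can do to a risk ratio.** All inputs are assumed: no treatment effect; 30% of subjects at 0.6% event risk and 70% at 0.15%; 70% cardioverted by day 7, except high-risk usual-care subjects at a lower share p.
- Apixaban risk in the group: (0.3×0.7×0.006 + 0.7×0.7×0.0015)/(0.21 + 0.49) = 0.00285
- Usual-care risk at p = 0.5: (0.3×0.5×0.006 + 0.7×0.7×0.0015)/(0.15 + 0.49) = 0.00255
- Risk ratio 0.00285/0.00255 = 1.12. With p = 0.6 it is 1.05, and with p = 0.3 it is 1.30.

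The true ratio is 1.00 throughout. This shows that the mechanism exists. It predicts neither size nor direction, and swapping the arms would reverse it.

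**The case against.** The strongest reply has four parts.

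First, a reader might infer that nothing in the plan answers the stated objective. The documents do not support that. Protocol section 2 and inclusion criterion 1 omit early, and the intention-to-treat analysis of all randomized subjects answers that wording directly.

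Second, subjects lost from the 7-day group are analysed elsewhere. Thrombus-positive subjects have their own sets (SAP 5.4), pre-cardioversion events have their own reporting period, and endpoints are also split by cardioversion status (SAP 8.2.4). This stands. It limits the harm, although none of those tables is the one labelled early.

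Third, seven days is a sensible operational divider. Protocol 1.2 expects most image-guided procedures within days and conventional ones after at least 3 weeks. That supports keeping the 7-day count as a description. It does not remove the selection.

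Fourth, the study is descriptive, without hypothesis tests or decision rules (SAP 4.1, 4.2). This lowers the stakes, but p-values are still planned.

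Two larger numbers are tempting and should not be used. One misplaced pre-cardioversion stroke is not a quarter of the 4 predicted events, because those 4 are predicted after cardioversion. A normal model gives 1 − Φ(4/5.6) = 24% beyond 7 days, but it also puts Φ(−3.0/5.6) = 30% of times below zero.

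**Conclusion.** The point holds in a limited form. The two documents define early cardioversion differently, the objective is inconsistent on the word, and the only subgroup carrying the label depends on post-randomization course. No planned analysis isolates the protocol's early strategy using information fixed at randomization.

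The group can look safer than the strategy; that it will is not shown. Different make-up by arm is possible in an open-label trial, but the documents contain nothing that demonstrates it. The only scale available is about 10% of image-guided subjects beyond day 7, resting on timing borrowed from another trial and a lognormal shape. The main intention-to-treat analysis is unaffected. This deserves a SAP correction and does not put the trial's main results in doubt.

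**What to change.** 1. Reconcile the objective wording, and the meaning of early cardioversion, across the protocol and SAP.
2. In SAP 8.2.4 and 8.2.5, rename the group 'cardioverted within 7 days of randomization', state whether spontaneous reversion counts, label it post-randomization and descriptive, and give no between-arm p-values for it.
3. Add a by-arm subgroup for every clinical endpoint on baseline arrhythmia duration (≤48 h versus >48 h or unknown). SAP 6.4 already lists duration in hours as a baseline variable. Use planned strategy only where it was recorded before randomization; the documents do not show that Visit 1 captures it, and a new field would not help subjects already randomized.

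Visit 2 imaging should not be the main way to derive strategy. A subject with >48 h duration who dies, has a stroke or reverts before imaging would be classed as conventional, which repeats the same selection. The new subgroup should not be ranked above the intention-to-treat analysis.

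The cost is SAP wording, a wording reconciliation in the protocol, and one more subgroup table with few events. Baseline duration only approximates the strategy: the >48 h or unknown stratum still includes conventional-strategy subjects, and the ≤48 h stratum may include image-guided ones. Its advantage is that the arms within each stratum remain a randomized comparison.

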**SCHEDULE OF ACTIVITIES**

The Schedule of Activities table provides an overview of the protocol visits and procedures. Refer to [Study Procedures](#) and [Assessments](#) sections of the protocol for detailed information on each procedure and assessment required for compliance with the protocol.

The investigator may schedule visits (unplanned visits) in addition to those listed on the schedule of activities, in order to conduct evaluations or assessments required to protect the wellbeing of the subject.

Procedure	Visit 1 Enrollment Screening/Randomization a	Visit 2 Cardioversion (or planned cardioversion)	Visit 3 Follow-Up (30 days post cardioversion (Visit 2) or up to 90 days following Visit 1) e
Visit Windows			±7 days
Informed Consent	X		
Obtain Alternative Contact	X		
Inclusion/Exclusion	X		
Demographics	X		
Medical History	X		
CHA 2 DS 2 -VASc score b	X		
Local Laboratory Parameters	X	X	X
Electrocardiogram	X (may be obtained on the day prior to Visit 1)	X	X
Randomization	X		
Cardioversion c		X	
Endpoint Assessments d		X	X
Dispense Study Drug	X	X	
Collect Study Drug		X	X
Study Drug Compliance Check		X	X
Adverse Event Assessment		X	X

a. Screening/Randomization could occur on the same day

b. CHA2DS2-VASc - Congestive heart failure, hypertension, age, diabetes, stroke, vascular disease, age, sex category risk score

c. Cardioversion details (timing, type, attempts, and rhythm status) and use of image guidance

d. Endpoints; stroke, systemic embolism, major bleeding, clinically relevant non-major bleeding, and all cause death

e. See Figure 2 for examples of timing of Visit 3.

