### 6.2. Visit 2 Cardioversion

The Investigator or designee will:

- Assess and record clinical endpoints (stroke, systemic embolism, major bleeding, clinically relevant non-major bleeding, and all cause death) and whether they meet the serious adverse event reporting criteria.
- Perform study drug treatment compliance check, see [Section 5.2.4](#).
- Assess and record local clinical laboratory parameters, including INR for VKA-treated subjects.
- Assess and record cardioversion details (timing, type, attempts, and rhythm status), and use of image guidance (eg, TEE/TOE or CT).
- Assess and record adverse events.
- Collect and dispense study drug treatment, if required, as per label and routine clinical practice, and visually confirm the subject has received their medicine supply, see [Section 5.2.2](#).

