#### **7.5. Details of Cardioversion**

The date and time of all attempted cardioversion procedures and rhythm status according to ECG analysis will be captured within the CRF at Visit 2 and Visit 3. The performance of ECG monitoring is in accordance with the investigator's usual practice, and it is expected this would be performed pre and post cardioversion procedures at appropriate times.

Attempts are defined as the number of times the subject is admitted for the cardioversion procedure and not the number of attempts during a single admission.

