2.1. Study Design

This is a randomized, active controlled, parallel-group, open label study. Approximately 1500 subjects will be randomized 1:1 to apixaban or usual care (parenteral heparin and/or oral anticoagulation with Vitamin K antagonist (excluding other novel oral anticoagulants)). Following randomization, endpoints will be collected during the 30 days following the early cardioversion or during the 90 days post randomization if cardioversion is not performed within that time frame.

A schematic diagram below (Figure 1) shows the design of the study:

Figure 1 Study Design Schematic

Figure 1 Study Design Schematic

The Schedule of Activities table provides an overview of the protocol visits and procedures. Refer to [Study Procedures](#) and [Assessments](#) sections of the protocol for detailed information on each procedure and assessment required for compliance with the protocol.

The investigator may schedule visits (unplanned visits) in addition to those listed on the schedule of activities, in order to conduct evaluations or assessments required to protect the wellbeing of the subject.

Table 1 Schedule of Activities

Procedure	Visit 1 Enrollment Screening/Randomization ^a	Visit 2 Cardioversion	Visit 3 Follow-Up (30 days post cardioversion (Visit 2) or up to 90 days following Visit 1) ±7 days
Visit Windows			
Informed Consent	X		
Obtain Alternative Contact	X		
Inclusion/Exclusion	X		
Demographics	X		
Medical History	X		
CHA ₂ DS ₂ -VASc score ^b	X		
Local Laboratory Parameters	X	X	X
Randomization	X		
Cardioversion ^c		X	
Endpoint Assessments ^d		X	X
Dispense Study Drug	X	X	
Collect Study Drug		X	X
Study Drug Compliance Check		X	X
Adverse Event Assessment		X	X

^a Screening/Randomization could occur on the same day

^b CHA₂DS₂-VASc - Congestive heart failure, hypertension, age, diabetes, stroke, vascular disease, age, sex category risk score

^c Cardioversion details (timing, type, attempts, and rhythm status) and use of image guidance

^d Endpoints: stroke, systemic embolism, major bleeding, clinically relevant non-major bleeding, all cause death, and length of in-hospital stay

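### SAP 8.2.5: the hazard ratio for time to first cardioversion attempt, image guided against not, uses a label recorded after the clock starts and cannot be read as an effect of imaging

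*SAP*

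**What the plan says.** SAP 8.2.5 (Other analyses) asks for a hazard ratio and p-value for "time from randomization to the first attempt at cardioversion, comparing image guided to non-image guided subjects". The population is everyone randomised: "The summary for first attempt will be based on the full analysis set". Subjects without an attempt stay in, "with time to first attempt censored at the last day of follow-up if an attempt has not been made".

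The grouping variable is collected later. Protocol 6.2 has the investigator, at Visit 2, "Assess and record cardioversion details (timing, type, attempts, and rhythm status), and use of image guidance". Footnote c to the schedule in SAP 2.1 attaches the same items to the cardioversion row, which is marked only under Visit 2: "Cardioversion details (timing, type, attempts, and rhythm status) and use of image guidance". Protocol 5.1 and 6.1 describe no stratification by imaging strategy and no Visit 1 record of it. Protocol 7.5 counts admissions: "Attempts are defined as the number of times the subject is admitted for the cardioversion procedure". A subject who reverts spontaneously without being admitted for the procedure therefore has no attempt.

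For clinical endpoints, SAP 8.2.4 defines three periods: before cardioversion, after cardioversion, and the whole study. SAP 8.2.5 then compares each endpoint between spontaneous and interventional cardioversion, and between electrical, pharmacological and both. It names the analysis set for these comparisons but not the period.

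**The concern.** A Cox model needs group membership to be known when the clock starts. Here it is known only at or near the event, and for subjects who never have an attempt the SAP does not say which group they join. If those without imaging are placed in the non-guided group, that group gains subjects who are censored late and cannot contribute an event. The ratio then exceeds 1 without any true difference.

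A second mechanism works even with perfect coding. Protocol 1.2 states that "An image-guided approach facilitates cardioversion earlier than the conventional minimum of 3 weeks", so the ratio largely restates the decision to follow one strategy or the other. A small p-value could be reported as a finding about imaging when it carries neither a randomised nor a baseline comparison.

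For the endpoint comparisons by type of cardioversion, the risk is unequal follow-up. In the whole-study period, follow-up from randomisation ends 30 days after cardioversion, so its length depends on when cardioversion took place. Protocol 9.1 predicts 1 + 3 = 4 stroke or embolism events and 2 + 5 = 7 major bleeds, so one or two events decide such a table.

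**Working it through.** The plan gives no figure for this analysis, so there is none to reproduce. The sizes below are illustrations on stated assumptions, not predictions.

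**1. No true effect.** Inputs: 60% of attempted subjects imaged, and a share p with no attempt (both assumed). Time to attempt is a mixture, assumed: five eighths exponential with mean 3 days, three eighths 21 days plus an exponential with mean 9.6 days. The two means, 3.0 and 21 + 9.6 = 30.6 days, are those quoted in Protocol 1.2 for the cited trial of echocardiography-guided cardioversion. Imaging is independent of timing. Subjects without an attempt are censored at day 90.

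If subjects without an attempt are never imaged and are coded non-guided, every guided subject has an attempt. In the non-guided group the share with an attempt is 0.4(1 − p) / [0.4(1 − p) + p]:
- p = 2%: 0.392/0.412 = 95%
- p = 10%: 0.36/0.46 = 78%
- p = 20%: 0.32/0.52 = 62%

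Cox hazard ratio, guided against non-guided, by how often subjects without an attempt are imaged:

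| No attempt | Never imaged, coded non-guided | Imaged half as often | Imaged equally often, or excluded |
|---|---|---|---|
| 2% | 1.2 | 1.1 | 1.0 |
| 10% | 1.9 | 1.4 | 1.0 |
| 20% | 2.9 | 1.6 | 1.0 |

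With 1500 subjects and 2% without an attempt, the first coding gives p < 0.05 in about 96 to 97% of null trials. With equal imaging it is about 5%.

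**2. Timing driven by strategy.** Same set-up, but guided subjects follow the 3-day distribution, and 20, 40 or 70% of non-guided subjects (assumed) follow the route of at least 3 weeks. The rest are early.

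| Non-guided on the 3-week route | All have an attempt | 2% no attempt, never imaged | 10% no attempt, never imaged | 10% no attempt, imaged half as often |
|---|---|---|---|---|
| 20% | 1.9 | 2.1 | 2.9 | 1.8 |
| 40% | 3.2 | 3.5 | 4.6 | 2.4 |
| 70% | 9.2 | 9.9 | 12.4 | 3.5 |

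Strategy alone gives 1.9 to 9.2. Coding of never-imaged subjects adds about 7 to 11% at 2% without an attempt and about 35 to 55% at 10%. With imaging half as often, the ratio falls below the all-attempted value in each of these rows, though at 20% without an attempt and 20% on the 3-week route it is 2.0 against 1.9. The direction of the coding effect is therefore not fixed.

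**3. Follow-up in the whole-study period.** For cardioversion on day T, planned follow-up is T + 30 days. Using the two quoted means only to show the scale, T = 3.0 gives 33 days and T = 30.6 gives 60.6 days, a ratio of 60.6/33 = 1.84 with equal risk per day. In the post-cardioversion period each subject has 30 planned days, ratio 1.0. How timing differs between types of cardioversion is not in the documents.

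**4. Spontaneous reversion.** Protocol 5.2.3 continues treatment to 30 days after Visit 2 for subjects who revert before the procedure. The Protocol Summary and Section 3 collect endpoints for 30 days after cardioversion, or for 90 days from randomisation if it is not performed, and do not mention spontaneous reversion. At equal timing T, follow-up relative to interventional cardioversion is 1.0 if spontaneous reverters are followed for 30 days from Visit 2 at T, and 90/(T + 30) if they are followed for 90 days (3.0 at T = 0, 1.5 at T = 30).

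**The case against.** The coding is an assumption. No passage says that subjects without an attempt become non-guided. Protocol 5.2.3.2 speaks of a subject scheduled for an image-guided strategy, the Protocol schedule allows Visit 2 to be a planned cardioversion, and Protocol 6.5 expects deferral after imaging that suggests thrombus. Subjects without an attempt can therefore carry the guided label, and the null bias disappears if they are imaged as often as the others. This stands. So does the objection that timing unrelated to imaging is unrealistic here. A reader might infer from the null results that a significant ratio would reflect coding alone. The documents do not support that: by their own account imaging brings cardioversion forward, and step 2 shows strategy dominating when few subjects lack an attempt.

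A reader might also infer that the endpoint comparisons have no period at all, or that the SAP contrasts subjects with and without cardioversion directly. Neither holds. SAP 8.2.4 supplies three periods and only the assignment is missing. Cardioversion status is a subgroup listing there, and no direct test of none against any is planned.

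On spontaneous reversion, the SAP lists it apart from no cardioversion, and the schedule counts Visit 3 from cardioversion at Visit 2. Both lean towards the 30-day reading. Figure 2 of the Protocol, which illustrates Visit 3 timing, is not shown in the text available and may settle it.

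Finally, the study is descriptive, with no decision rule. That limits the weight of the point but does not remove it, because SAP 8.2.5 still asks for the ratio and p-value.

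**Conclusion.** The point holds in limited form. The planned ratio uses a label recorded after time zero, with no coding rule for subjects without an attempt. It combines choice of strategy with labelling and cannot be interpreted as an effect of imaging. The null bias of about 1.2, 1.9 and 2.9 rests on 60% imaged, timing unrelated to imaging, and never-imaged subjects coded non-guided. It is absent under equal imaging or exclusion, and its size and direction vary once timing follows strategy.

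The secondary point is an unassigned period and an unstated date for spontaneous reversion in the comparisons by cardioversion type. Its size and direction cannot be determined from the documents. A reader might take all this to weaken the trial's main results. It does not: the comparison of randomised arms is untouched. Minor to moderate.

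**What to change.** In SAP 8.2.5:

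1. Delete the hazard ratio and p-value by image guidance. Report time to first attempt by randomised arm, with the Kaplan-Meier and hazard ratio methods already in SAP 8.1.2.
2. Describe timing by guidance among subjects with an attempt. List subjects without an attempt separately, imaged and not imaged. Label the output as non-randomised.
3. Assign the comparisons by cardioversion type to the existing post-cardioversion period, 30 days from first cardioversion. State which date anchors spontaneous reversion, and list earlier events separately.
4. Reconcile Protocol 5.2.3 with the Protocol Summary and Section 3 on follow-up of spontaneous reverters, checking Figure 2.

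The cost is SAP wording and a little programming, because Protocol 7.5 already captures the date and time of every attempt. One planned ratio is lost and a few early events move to a separate listing. If only the Visit 2 date is available for a spontaneous reversion, events between reversion and that visit fall before the anchor, so the listing is needed.
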